15.5. Extent of Study Drug Exposure

Study treatment exposure will be summarized using the Safety Population.

Analyses for the extent of exposure will focus on the duration of each respective treatment (migalastat, ERT, or untreated). Duration will be defined as:

$$Dur = End\ date\ of\ treatment - start\ date\ of\ treatment + 1$$

Breaks in therapy or discontinuation in exposure as well as switching therapy will be accounted in the calculations. Missing dates will be imputed as described in Section 6.1. Exposure will be calculated after the dates are imputed.

Extent of exposure (in days) will be compared between the treatment groups using the Wilcoxon Rank Sum test. In addition, the number of patients treated at each visit will be presented by treatment group.

Other summaries which will be presented are average dose (mg) per time period (3 months), ongoing status (yes, no, unknown) and primary reason for interruption/discontinuation (adverse drug reaction, lack of efficacy, disease improvement, patient/guardian decision, investigator decision, pregnancy and/or breast feeding).

All exposure parameters will be included in a by-patient listing.

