## **Rationale and background**

Fabry disease is a rare X-linked lysosomal disorder in lysosomes, resulting in a multisystemic disorder caused by deficiency in the enzyme  $\alpha$ -galactosidase A ( $\alpha$ -Gal A) due to mutations in the GLA gene, encoding the hydrolase  $\alpha$ -Gal A enzyme, which catalyses glycosphingolipids namely globotriaosylceramide (Gb3). Reduced or absent  $\alpha$ -Gal A activity leads to accumulation of Gb3 in the lysosomes of various organs, as well as cellular dysfunction and inflammation causing physical symptoms and eventual organ failure (1,2). Fabry disease as an X-linked disorder with a high penetrance, though not 100% in female heterozygotes, although the disease affects both males and females. With the X-linked nature, Fabry disease is suitable for an efficient, high diagnostic yield cascade screening over at least three generations surrounding an index-patient. The Danish National Fabry Centre has now more than 20 years of experience of cascade screening, which has provided a patient population of 115 male and female patients. The prevalence of Fabry disease in the Danish population is estimated to be 1:58000 (males 1:85000, females 1:44000) (3).

Primarily male patients, with early onset classical phenotypes have none or very low  $\alpha$ -Gal A activity, and they inevitably develop multiorgan failure without treatment (4). Patients with late onset of Fabry disease represent both males and females with higher  $\alpha$ -Gal A activity and variable degrees of organ involvement (5). Fabry disease can cause irreversible damage to multiple organs resulting in Fabry associated clinical events (FACEs) such as renal, cardiac, cerebrovascular events, and death (5).

The primary Fabry specific therapy has historically been enzyme replacement therapy (ERT), and as of 2016 an oral chaperone therapy, Migalastat, has been available, providing an alternative to ERT for patients with amenable mutations by increasing their endogenous  $\alpha$ -Gal A enzyme activity (6–14). However, real-world long-term data from well-characterised cohorts with available detailed clinical consecutive observations with focus on treatment with Migalastat and Fabry associated events has not been fully investigated (12–14).

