15.1. Approach to Safety Analyses

As this is an observational study, patients may switch or stop therapies. In the Safety Population, analysis will present results based on the actual exposure, ie, treatment group at the time of the event (migalastat, ERT, or untreated). As patients can stop or switch therapy while enrolled in the study, they might be counted more than once in the analysis.

Serious adverse events will be analysed as described in Section 13 for the composite FACES.

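### The rank sum test on days of exposure (SAP 15.5) assumes independent groups, but the groups share patients, so its p-value does not have its nominal error rate

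*SAP*

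**What the plan says.** SAP 15.5 defines exposure as the days from start to end of each respective treatment, with untreated time as a third category beside migalastat and ERT. It sets the analysis population: "Study treatment exposure will be summarized using the Safety Population". It adds: "Breaks in therapy or discontinuation in exposure as well as switching therapy will be accounted in the calculations". It then plans the test: "Extent of exposure (in days) will be compared between the treatment groups using the Wilcoxon Rank Sum test". It does not say which pairs of the three groups are tested. SAP 3.2 puts all comparisons other than the primary one at two-sided 0.05 without adjustment.

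SAP 15.1 says how patients are assigned to groups for safety: "In the Safety Population, analysis will present results based on the actual exposure". It continues: "As patients can stop or switch therapy while enrolled in the study, they might be counted more than once in the analysis".

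The protocol's Rationale and background says that "as of 2016 an oral chaperone therapy, Migalastat, has been available". It describes ERT as the historical therapy but gives no date for it.

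**The concern.** The Wilcoxon rank sum test takes its null distribution from independent observations in separate groups. A patient who moves from untreated to ERT and then to migalastat supplies a value to each group, and those values are linked because one period ends where the next begins. A p-value computed as if they came from different people is not calibrated.

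The groups also had different calendar time in which to accrue exposure. A small p-value printed beside the reasons for discontinuation could be taken to mean that patients stay longer on one treatment than on another, which the test does not show.

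**Working it through.** The SAP gives no expected exposure, group sizes or switching rate for this test, so there is no planned figure to reproduce.

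**Step 1: do the groups share patients?**
- SAP 2: all patients are treatment naïve at diagnosis.
- SAP 5.1: those who start treatment within 3 months of enrolment count as treated from the outset. Anyone who starts later has untreated time as well as treated time.
- SAP 6.1: therapy can change more than once in the 20-year period.
- SAP 15.1: results follow actual exposure, with repeat counting accepted.
- Nothing in SAP 15.5 or elsewhere limits this test to one record per patient, to the initial group or to non-switchers, and no method for dependent data is named.

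So overlap is allowed and likely. Its extent is not given.

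**Step 2: what does overlap do to the size?** Assume two equal groups with the same exposure distribution, a share f of patients in both, and within-patient correlation ρ between the two exposures. The variance of the group contrast is then about (1 − fρ) times what the test assumes, and

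size ≈ 2 × [1 − Φ(1.96 / √(1 − fρ))].

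For f = 1 and ρ = −0.9: 1.96/√1.9 = 1.42, size 0.155. For f = 1 and ρ = +0.5: 1.96/√0.5 = 2.77, size 0.006.

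| Overlap f | ρ = −0.9 | ρ = −0.5 | ρ = +0.5 |
|---|---|---|---|
| 25% | 0.077 | 0.065 | 0.036 |
| 50% | 0.104 | 0.080 | 0.024 |
| 100% | 0.155 | 0.110 | 0.006 |

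Simulation (20 or 30 per group, 4000 runs) agrees: at full overlap it gives 0.152 to 0.154 for ρ = −0.9 and 0.007 to 0.011 for ρ = +0.5. With ρ = 0 it gives 0.043 to 0.054. If every patient divides follow-up at random between two groups, simulated size is about 0.10 when follow-up varies from 5 to 22 years and about 0.16 when it is equal for all.

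Follow-up of fixed length split between treatments pushes ρ negative and the test too liberal. Follow-up that differs between patients pushes ρ positive and the test too conservative.

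**Step 3: calendar limits.** Take migalastat as available from 1 January 2016 (the protocol gives only the year). Follow-up begins on 1 January 2001 and ends on 31 December 2022 (protocol, Method) or in December 2023 (SAP 2, taken as 31 December).
- Migalastat: 2557 days (7.0 years) or 2922 days (8.0 years).
- Whole window: 8035 days (22.0 years) or 8400 days (23.0 years).

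**Step 4: how far could calendar time alone drive a migalastat-ERT difference?** Independent patients were simulated (2000 runs) with the same discontinuation hazard on both drugs, starts uniform over each availability window, and ERT available from 2001 or 2006. The hazards, group sizes and ERT years are all assumptions. Rejection rates at nominal 0.05:

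| Discontinuation per year | 30 ERT vs 20 migalastat | 20 ERT vs 10 migalastat |
|---|---|---|
| 0 | 95 to 99.7% | 75 to 93% |
| 5% | 63 to 88% | 38 to 60% |
| 10% | 38 to 61% | 19 to 35% |
| 20% | 15 to 24% | 9 to 14% |

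The effect can be large or modest, depending on inputs that the documents do not supply.

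**The case against.** The strongest reply is that this is a minor safety table, and that several stronger readings go beyond the documents. Four of those deserve an answer.

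- *The test mainly measures drug availability, through a built-in three-fold difference.* The ratios 22/7 = 3.1 and 23/8 = 2.9 compare theoretical maxima and need ERT to have been available from 2001, which is not stated. If it began in 2006, the ratios are 17/7 = 2.4 and 18/8 = 2.3. Patients also enter throughout the window, and untreated time is bounded by treatment start rather than by drug availability. Nor is 2016 a firm lower limit: the protocol's reference list includes 18-month randomised migalastat results published in April 2017, so trial exposure before 2016 existed, although the documents do not say whether anyone in this cohort had it.
- *Ongoing exposure is wrongly treated as complete.* For extent of exposure, the days accrued to cut-off are fully observed. Censoring matters only if the question is persistence, which SAP 15.5 does not claim to measure. The section also tabulates ongoing status and reasons for discontinuation.
- *The test gives too many false positives.* Step 2 shows that the error can go in either direction.
- *Repeat counting concerns events only.* SAP 15.1 does speak of the group at the time of the event. But SAP 15.5 uses the same population and takes switches into account in the durations, so the same overlap arises.

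The objection stands on availability, censoring and direction. It does not remove the independence problem.

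**Conclusion.** The planned test is wrong as written. An independent-samples test is applied to groups that the SAP's own rules allow to share patients, so its p-value does not have the nominal 5% error rate. The range of 0.006 to 0.155 rests on assumed overlap (25 to 100%) and correlation (-0.9 to +0.5); with no overlap or no correlation, size returns to about 0.05. Calendar limits may add to a migalastat-ERT difference, by an amount that cannot be fixed from the documents.

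The consequence is small. A reader might infer that effectiveness or safety conclusions are compromised, but they are not. The primary FACE analysis (SAP 13.1), the SAE incidence rates (SAP 15.3) and overall survival (SAP 15.4) do not use this p-value. SAE rates do use the exposure durations, but the durations themselves are not in question here.

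**What to change.** Delete the sentence in SAP 15.5 that specifies the rank sum test. For each treatment, report the number of patients, person-years, median and range. SAP 7.3 already provides counts, medians, minimums and maximums, so person-years is the only addition. This matches SAP 13.1.1, which plans descriptive statistics only for the per-period time-to-event summaries in which a patient can be counted more than once.

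State that the exposure summary is not to be read as persistence. If persistence is of interest, present time on each treatment with ongoing exposure censored at the data cut-off.

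The cost is one deleted sentence and a small change to one table. No stated objective depends on the test.

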15.6. Clinical Laboratory Tests

Analyses of clinical laboratory assessments will focus on serum creatinine, urine protein, urine albumin, and urine ACR. Other labs results will be provided in by-patient listings. Analysis will be done using the same methodology as for eGFR (Section 13.7).

Data will be summarized using descriptive statistics will be displayed for change from Analysis Start Date (time of diagnosis or treatment start) to e.g. time points such as the date of the first treatment switch, date of the treatment to migalastat or any other time points of interest.

Analysis Methods

Data will be listed. Listings will contain flags indicating therapy change. Spaghetti plots will indicate what treatment group a patient was on at the time of measurement.

In the Safety Population, data will be analyzed from the time of diagnosis.

For dialysis and transplant patients, the Analysis Start Date creatinine (as it is done for eGFR in Section 13.7) will be reset to the last value before dialysis start or before transplantation and used thereafter.

All laboratory data, values, units, normal reference range, and out-of-range flags collected in the clinical database will be included in by-patient listings for further medical review.

The analysis will address data based on the actual exposure. The count of out of range values as well as counts of clinically significant results will be presented by treatment.

Summaries of out of range values and shift tables (using Analysis Start Date as baseline) could be prepared for timepoints of interest such as e.g. start of migalastat therapy. .

An additional table showing if a test result was out of range at any measurement over time will be prepared. A similar table will be prepared for potentially clinically significant values.

15.7. Vital Signs

Vital signs will be analyzed in the same way as clinical laboratory tests (Section 15.6).

Vital signs will also be collected at the time of a serious adverse event.

Those values will be included in a table that presents if a test result was out of range at any measurement. A similar table will be prepared for potentially clinically significant values.

15.8. Body Weight

Body weight will be analyzed in the same way as clinical laboratory tests (Section 15.6).

15.9. Electrocardiogram

Echocardiograms will be analyzed in the same way as clinical laboratory tests (Section 15.6).

15.10. Echocardiogram

Echocardiograms will be analyzed in the same way as clinical laboratory tests (Section 15.6). Echocardiogram parameters include LVMi, ejection fraction, fractional shortening, left ventricular internal diameter end diastole and end systole, midwall fractional shortening, and wall thickness. Echocardiograms will only be required if they are medically necessary.

15.11. Male Infertility

To show the occurrence of male infertility, a summary will be provided using binary variable (Yes/No) by treatment group and overall. Treatment group at enrollment will be utilized.

A listing will also be provided displaying the above information.

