### *Registration of treatment*

All patients included in the trial are considered treatment naïve at inclusion in the observational period (01.01.2001). Registration of initiation, change or cessation of treatment will follow the following structure:

Date (Date)	Drug (Name)	Action* (Categorical)	Dose (Integer)	Dose interval (Comment)	Comment (Comment)
----------------	----------------	--------------------------	-------------------	----------------------------	----------------------

\*Action is restricted to four levels: initiation, increase, decrease, cessation.

Cardiac events		
Date of event	Cardiac event	Yes/No
	Myocardial infarction	Yes No
	Unstable angina pectoris	Yes

		No
	PCI / CABG	Yes No
	Heart Failure	Yes No
	Arrhythmia (New onset of symptomatic arrhythmia requiring anti-arrhythmic Medication)	Yes No
	Heart procedure (pacemaker/ICD/valve surgery)	Yes No

Renal events		
Date of event	Renal event	Yes/No
	Doubling of s-creatinine	Yes No
	ESKD	Yes No

Cerebrovascular events		
Date of event	Cerebrovascular event	Yes/No
	Stroke	Yes No
	TIA	Yes No

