2. OVERVIEW OF STUDY DESIGN

This is a retrospective study of prospectively collected patient data with the use of secondary patient data from both paper and electronic patient files. All patients are treatment naïve at time of diagnosis. Both migalastat and ERT will be studied retrospectively. Also untreated patients will be studied by assessment of relevant clinical and laboratory variables. The analysis will originate at the time of diagnosis.

The patients have been followed for more than 20 years from 2001 until December 2023. All identified patients with Fabry disease, whether receiving specific Fabry medication or not, have been offered annual or biannual thorough workups including examinations of Fabry associated organ function and symptoms. The study will be carried out at the Danish National Fabry Centre, Department of Endocrinology, Copenhagen University Hospital.

All patients from the Danish National Fabry Centre will be included. Subgrouping is aimed at depending on available numbers: non-amenable, amenable, classic, non-classic, males, females, treated including type of treatment or untreated.

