5. DEFINITION OF PATIENT POPULATIONS TO BE ANALYZED

5.1. Safety Population

The Safety Population will include all patients with Fabry disease who consented to participate and enrolled in the study. Patient disposition and reason for discontinuations will be presented in the Safety Population.

Patients who enter the study as untreated but switch to a treatment (migalastat or ERT) within 3 months from enrollment will be considered in analysis as initially belonging to a treatment group they switched to. Depending on an analysis as further discussed the group assignment might change in the case of a treatment switch.

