11. DEFINITION OF STUDY TIME POINTS

11.1. Definition of Diagnosis Date

Enrollment is the date on which the patient was diagnosed with the Fabry disease. For analysis of assessments which were not collected on the diagnosis date, the assessment closest to the diagnosis date will be utilized. If there are 2 assessments that are equidistant from the diagnosis date, then the assessment prior to diagnosis will be utilized.

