15.12. Pregnancy

A summary on the pregnancy status (Yes/No) by treatment group and overall will be provided. Treatment group at enrollment will be utilized.

A listing will also be provided displaying the above information.

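### SAP 15.11 (and 15.12, if it covers follow-up) groups cases by treatment at diagnosis, so infertility or pregnancy in later starters and switchers falls in the wrong treatment column

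*SAP*

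**What the plan says.** SAP 15.11 gives a yes/no summary of male infertility by treatment group and overall, and fixes the group: "Treatment group at enrollment will be utilized". SAP 15.12 does the same for pregnancy: "A summary on the pregnancy status (Yes/No) by treatment group and overall will be provided", followed by the same sentence on enrollment. The listing in each section repeats only what is in the table.

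What enrollment means is set elsewhere in the SAP:

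- Section 11.1: "Enrollment is the date on which the patient was diagnosed with the Fabry disease".
- Section 2: "All patients are treatment naïve at time of diagnosis". The protocol says the same under Method, and under Registration of treatment it calls all patients naive at inclusion.
- Section 5.1 makes one exception. Untreated entrants who "switch to a treatment (migalastat or ERT) within 3 months from enrollment will be considered in analysis as initially belonging to a treatment group", namely that of the therapy begun. It adds: "Depending on an analysis as further discussed the group assignment might change in the case of a treatment switch".

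The general rule for safety is in section 15.1: "analysis will present results based on the actual exposure", meaning the treatment at the time of the event. The same section accepts that a patient may be counted more than once.

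**The concern.** The SAP's own definitions place almost nobody in a drug column on the enrollment date. The 3-month rule is the only stated way in. Follow-up lasts some 20 years, and SAP 6.1 expects patients to change therapy, some more than once. A label fixed at diagnosis takes no account of this.

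Infertility and pregnancy under treatment are safety questions about exposure. If a case that arose on drug is shown as untreated, the drug column is too low and the untreated comparison is too high, and both errors favour the drug. If it is shown under a previous drug, it is charged to the wrong product. Migalastat is the study's focus and has been available only since 2016 (protocol, Rationale and background), so patients diagnosed well before then can reach it only by a later start or a switch.

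**Working it through.** No figure in the plan needs reproducing, because the point concerns how a descriptive table is grouped. The check compares the column that 15.11 and 15.12 assign with the column that 15.1 would assign.

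**Inputs.** Group fixed at enrollment (15.11, 15.12); enrollment = diagnosis (11.1); all naive at diagnosis (2); reassignment if therapy starts within 3 months (5.1); actual exposure at the event (15.1).

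The last sentence of 5.1 lets the group change in some analyses, as discussed later in the SAP. For these two tables the later discussion says enrollment, so no change applies.

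| Patient history | Column under 15.11/15.12 | Column under 15.1 | Agree? |
|---|---|---|---|
| Never treated, event at any time | Untreated | Untreated | Yes |
| Starts within 3 months, event on that first drug | That drug | That drug | Yes |
| Starts after 3 months, event before the start | Untreated | Untreated | Yes |
| Starts after 3 months, event on drug | Untreated | The drug | No |
| Starts ERT within 3 months, switches to migalastat, event on migalastat | ERT | Migalastat | No |
| Starts within 3 months, stops, event while off drug | The drug | Untreated | No |

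**Size.** Let f be the share of treated patients who start within 3 months of diagnosis. The documents do not give f. The share of treated patients whose on-drug events fall under untreated is 1 - f:

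- f = 0: 1 - 0 = 100%
- f = 0.5: 1 - 0.5 = 50%
- f = 1: 1 - 1 = 0%

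At f = 1 the last two rows of the table remain wrong, so the rule still fails for patients who switch or stop.

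**Patients concerned.** SAP 4 expects about 115 patients, one third male: 115 / 3 = about 38 males for 15.11 and 115 x 2/3 = about 77 females for 15.12.

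**Other safety outputs.** SAEs are summarised by treatment at the time of the event (15.2), and laboratory data are analysed by actual exposure (15.6). The protocol, under Study treatment, also groups patients who switch by their current treatment at the time of assessment, and SAP 17.1 declares no change from the protocol. Sections 15.11 and 15.12 depart from all of these and give no reason.

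**The case against.** **The 3-month rule.** A reader might infer that every case on drug is counted as untreated, or that a signal could never show in a drug column. The documents do not support either. Section 5.1 moves early starters into a drug group, so a case on their first drug is correctly placed. An early ERT starter who switches is counted under ERT, not as untreated. This limits the point to later starters and to patients who switch or stop; it does not remove it.

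**Baseline status may be all that is meant.** Grouping at enrollment would then be coherent. For infertility this does not fit. Section 3.2.2 lists its occurrence as a safety endpoint, 15.11 uses the same term, and baseline fertility status is already reported under 9.1. For pregnancy the objection has force. Section 15.12 speaks of status, pregnancy is not among the endpoints in 3.2.2, and 9.1 covers it at baseline. If baseline is intended, 15.12 is consistent but repeats 9.1, and the plan has no dedicated by-treatment pregnancy table for follow-up.

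**The naive premise is not the SAP's only position.** Section 6.1 derives treatment duration before enrollment, and section 10 tabulates prior ERT and migalastat exposure. This conflicts with sections 2 and 11.1 and must be reconciled. It does not rescue the tables, since events after a later start or switch would still be misplaced.

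**Other outputs limit the harm.** Congenital anomalies and hospital admissions qualify as SAEs and are attributed by treatment at the event (15.2). Pregnancy is recorded as a reason for stopping therapy (15.5). That stands for serious outcomes, but not for infertility or pregnancy that does not meet the SAE definition.

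**Conclusion.** The point holds for male infertility, and for pregnancy if 15.12 is meant to cover follow-up. As written, events on drug in patients who start more than 3 months after diagnosis are counted as untreated. Events in early starters after a switch are counted under the earlier drug. Both contradict 15.1.

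The conclusion rests on the SAP's statements that enrollment is diagnosis and that all patients are naive then. Its size depends on f and on how many patients switch or stop; neither is in the documents, so it could be large or small.

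A reader might try to size it from the share of the study period before migalastat became available. That is a share of calendar time, not of patients, because no diagnosis counts by year are given. It would also include never-treated and non-amenable patients, who may be correctly placed, and it says nothing about ERT.

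These are small descriptive tables without a test, and the primary endpoint is unaffected. The correction is worth making because the rule is wrong as stated and specific to put right.

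**What to change.** 1. In 15.11 and 15.12, replace the sentence on enrollment with text to this effect: *Events during follow-up are classified by treatment at the time of the event (infertility: onset, or first record; pregnancy: conception, or first record). A patient may be counted under more than one treatment, as in Section 15.1.*
2. Show treatment at the event in both listings.
3. Where the event date is missing, report the case in a separate category, treatment at event unknown, with the treatments ever received.
4. State whether 15.12 covers follow-up or baseline. Keep baseline pregnancy and fertility status in 9.1.
5. Reconcile the text in 6.1 and 10 that assumes therapy before enrollment with the treatment-naive statement in section 2.

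**Cost.** Treatment dates are already recorded (protocol, Registration of treatment). Dates of infertility onset, conception or pregnancy are not among the variables listed in the protocol, so they must be extracted from the records where available. Some, infertility onset above all, may not be recoverable, which is why item 3 is needed. The rest is SAP wording.
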